Unregulated cannabis, opioid, cocaine, or benzodiazepine use in the past 30 d	SQ, U

records, pharmacy records, and blood and urine samples (see Table 8). Our primary independent variable will be the initial soft-gel product obtained

from the medical cannabis dispensary, and our primary outcome will be self-reported pain severity using the Brief Pain Inventory severity subscale.

2.A. Settings: Montefiore Health System (Montefiore) is the largest healthcare system in the Bronx, NY with 11 hospitals and over 200 community clinics. Directed by [name] (Primary Mentor), the Montefiore Medical Cannabis Program includes 2500 patients certified by 25 physicians; approximately 25% of patients are PLWH. Vireo is a medical cannabis company with dispensaries in 11 states; two dispensaries are located in the NYC area. As of August 2020, in NY, Vireo served over 30,000 unique patients. Vireo staff will refer potential participants to the study and facilitate study retention; recruitment will occur at dispensaries.

2.C. Research visits and data collection.

Eligibility criteria. *Inclusion criteria* are: 1) ≥ 18 years old; 2) diagnosis of HIV 3) fluency in English; 4) actively certified for medical cannabis (medical records); 5) no medical cannabis dispensed in 60 days or used within the previous 30 days; 6) intent to have new soft-gel capsule product dispensed at Vireo (PMP or medical record); 7) ICD-10 diagnosis code for neuropathic pain, OR neuropathic pain in problem list of electronic medical record, OR neuropathic pain per medical cannabis certification form, OR Neuropathic Pain Questionnaire Short Form >0 .

Exclusion criteria are: 1) inability to provide informed consent; 2) inability to complete 14 weeks of study visit; 3) medical cannabis use within 30 days prior to enrollment; 4) unique pain symptoms (e.g. multiple sclerosis, rheumatoid arthritis); 5) terminal illness; 6) current or prior psychotic disorder; 7) unregulated cannabis, opioid, cocaine, or benzodiazepine use in the past 30 days (self-report and urine drug screen); 8) dispensed opioids or benzodiazepines within 60 days of enrollment; 9) non-steroidal anti-inflammatory (NSAID) use within 7 days prior to enrollment; 10) steroid use within the past 14 days with duration of therapy >21 days; 11) COVID vaccination within 14 days of screening.

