In-person visits: Participant's 2 in-person visits will occur in private rooms at the Montefiore/Einstein ICTR Clinical Research Center. At the baseline visit, study staff will describe the study and obtain written informed consent. Tracking forms as well as agreements to release medical, pharmacy, and PMP records will be completed. Participants will receive a refillable debit card for compensation. At all in-person visits, we will administer questionnaires, and collect blood and urine samples. Participants will receive \$27.50 for each in-person visit.

Phone or web visits will occur weekly over 14 weeks and include brief (5-7 minute) questionnaires administered by study staff over the phone or completed on-line. A total of 15 visits will occur, the first at baseline, when participants can be trained on how to complete it, and then one at the end of each week of the follow-up period. Participants will receive \$3 on debit cards after completing each phone or web-based questionnaire.

Blood draws will occur at week 0 and 14 in-person visits. They will measure VL, CD4 count, pro- and anti-inflammatory cytokines. Participants will be compensated an additional \$15 for each visit in which there is a blood draw.

Main independent variable will be the soft gel capsule product dispensed at Vireo, including a 1) high THC capsule, or 2) high CBD capsule. Other key independent variables will be cumulative THC and CBD taken (weeks 3-14, continuous measures).

Main outcome variables: Our primary outcome is pain severity, measured via the BPI severity scale (ordinal variable), as recommended by a committee of international pain experts.⁹² It is an 11-point (0-10) numerical rating scale of pain intensity, where 0 is 'No pain' and 10 is 'Pain as

bad as you can imagine'. Participants will complete the BPI severity scale in each phone visit (baseline and at each weekly visit).

Pro- (TNF α , IL-1 β , IL-6) and *anti-* (IL-4, IL-10) *inflammatory cytokines (secondary outcomes;* 0, 14 week *blood draws*) will be measured with Luminex assay and reported as picograms per mm 3 (continuous measure).

Adverse events (secondary outcomes) will be ARV adherence (AIDS Clinical Trial Group [ACTG] Adherence Interview,^{93,108} Adherence Visual Analog Scale [VAS; weekly]),⁹⁴ VL suppression (blood draws at 0, 14 weeks; copies/mL); and psychological symptoms—depression (CES-D; 0 and 14 weeks),⁹⁵ anxiety (GAD-7; 0 and 14 weeks),^{96,94,97,109}

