Other key outcome variables will be alternative pain measures (painDETECT,⁸⁴ pain catastrophizing⁹⁸).

Other measures that have strong associations with medical cannabis use or neurologic pain will be measured, including biological sex, substance use, quality of life, HIV risk behaviors, symptoms of post-traumatic stress disorder (PTSD), insomnia and medical comorbidities (Table 8).

3) Study Population

3.A. Sample size and power

determination. For our primary analysis (Aim 1), we based our power analysis on proportion of participants with clinically significant change in BPI pain severity scale (30% reduction) in each condition.^{8,48} We will recruit 100 participants in total; we anticipate that approximately 50 will use high THC soft gel

capsules and 50 will use high CBD soft gel capsules. Conservatively assuming 15% attrition in each arm, 42 participants will be in each arm. Because the individual-level intra-class correlation coefficient (ICC) associated with change in pain severity over time is unknown, we conducted simulation studies with varying ICC values, i.e., 0.2, 0.3, and 0.4. We present power calculations for pain severity in Table 9. Based on prior studies,^{47,48} we predict that 40% of those using high THC capsules will experience clinically significant reduction in pain and 20% of those using high CBD capsules will experience clinically significant reduction in pain.¹¹⁰ We will have 84% power at a significance level of 5% (two-tailed test) to detect a 20% difference in proportion of participants who achieve clinically significant reduction in pain during the follow-up period between high THC soft-gel capsules (40%) and high CBD (20%) soft gel capsules. We will have greater power to detect a larger difference or when ICC is lower.

For analyses with continuous dependent variables (Aim 2-3), a sample size of 42 participants/arm will allow us to have >90% power to detect a moderate effect size (i.e., Cohen's $d=0.5$) under a more stringent condition (ICC=0.4). We will have greater power when the effect size is larger or when ICC is lower.

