3.B. Eligibility criteria are described in Table 4. There are no eligibility restrictions based on gender, race or ethnicity. The study population is expected to reflect the racial and ethnic composition of PLWH receiving medical cannabis in the Bronx, NY. We estimate participants' characteristics based on the characteristics of patients receiving care in the collaborating medical cannabis dispensaries and having been certified at Montefiore. Taken together, characteristics from these sites are approximately: 60% men, 15% Hispanic, 40% non-Hispanic white, 30% non-Hispanic black, 13% non-Hispanic Asian, and 2% non-Hispanic other race. Thus, we expect to enroll the following participants: 40 women, 60 men; 15 Hispanic, 85 non-Hispanic; 40 non-Hispanic white, 30 non-Hispanic black, 13 non-Hispanic Asian, 2 non-Hispanic other race (see Targeted/Planned Enrollment Table).

Justification for the exclusion of minors.

Table 9. Power calculation for Aim 1

	High THC capsules	High CBD capsules	Power
ICC=0.2	40%	15%	>0.99
ICC=0.3	40%	15%	0.99
ICC=0.4	40%	15%	0.96
ICC=0.2	40%	20%	0.97
ICC=0.3	40%	20%	0.91
ICC=0.4	40%	20%	0.84

We will not include children under the age of 18 in our study population because: a) neuropathic pain in PLWH is much more common among adults, and b) the vast majority of providers at Montefiore who certify patients for medical cannabis use provide care only for adult patients. We expect that the age range of participants will be similar to that of patients certified for medical cannabis at Montefiore. Taken together, the median age of patients seen for medical cannabis visits was 51 years, and ranges from 19 years to 94 years. This correlates well with the population of PLWH in the US, in which more than 40% are 50 years old or over¹

3.C. Data sources: *Questionnaires:* At in-person research visits, research staff will administer questionnaires using Audio Computer-Assisted Self Interview (ACASI) technology; participants will enter responses directly onto computers. During phone visits, study staff will administer questionnaires and enter answers directly into the computer. Questionnaires will focus on pain, dose of THC and CBD in medical cannabis taken, psychological symptoms, and ARV adherence (Table 3).

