Aim 1: Examine how medical cannabis use affects self-reported pain. H1: The effect of medical cannabis use on self-reported pain-severity will differ by THC/CBD content. The primary outcome will be change in BPI pain severity scale (ordinal variable, 0-10; measured at baseline and weekly for 14 weeks). A clinically significant change is 30% reduction in BPI pain severity scale.⁹² Secondary measures will include BPI pain interference scale and neuropathic pain (painDETECT). We will compare the proportion of participants who achieve clinically significant change in pain at 14 weeks between those who use high THC soft gel capsules and those who use high CBD soft gel capsules. BPI pain interference scale and painDETECT will be compared between those using high THC vs high CBD as well. We will use mixed-effects logistic regression to test the effect of study arm on pain relief across the course of the study. Results will be adjusted for covariates associated with the outcomes of interest on bivariate testing. We will repeat this model using alternative measures of medical cannabis (cumulative dose of THC and CBD).

Aim 2: Examine how medical cannabis use affects pro- and anti-inflammatory cytokines. H2: Medical cannabis that has higher THC content will have greater reduction in pro-inflammatory

cytokines ($TNF\alpha$, $IL-6$). *H3: Medical cannabis that has higher CBD content will have greater increase in anti-inflammatory cytokines ($IL-4$, $IL-10$).* We will examine how pro- and anti-inflammatory cytokines measured at 0 and 14 weeks change in participants using high THC products versus high CBD products. We will use mixed-effects linear regression analyses to examine intervention and time effects as well as intervention-by-time interactions. This approach is appropriate in the event that the pro- and anti-inflammatory cytokine data show a non-normal distribution. We will repeat this model using alternative measures of medical cannabis (cumulative dose of THC and CBD). We will adjust for other chronic conditions that may lead to change in inflammatory cytokines, such as obesity, cardiovascular disease, and diabetes.

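### Entry sets no minimum BPI score, yet the Aim 1 responder outcome depends heavily on baseline BPI, and baseline BPI is not a guaranteed covariate

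*Combined protocol and SAP*

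**What the plan says.** **Entry.** Inclusion criterion 7 (section 2.C and Table 4) is met by any one of four routes. Three are record entries: "ICD-10 diagnosis code for neuropathic pain, OR neuropathic pain in problem list of electronic medical record, OR neuropathic pain per medical cannabis certification form". The fourth is a screening questionnaire: "Neuropathic Pain Questionnaire Short Form >0". Section 3.B adds nothing further ("3.B. Eligibility criteria are described in Table 4"). No inclusion or exclusion criterion mentions a BPI score.

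**Outcome.** Section 2.C describes BPI severity: "It is an 11-point (0-10) numerical rating scale of pain intensity, where 0 is 'No pain". Section 7.A, Aim 1, names the outcome: "The primary outcome will be change in BPI pain severity scale (ordinal variable, 0-10; measured at baseline and weekly for 14 weeks". It then sets the responder threshold: "A clinically significant change is 30% reduction in BPI pain severity scale". The groups are compared on the proportion of responders at 14 weeks, and a mixed-effects logistic model tests pain relief over the study. Section 3.A bases power on the same quantity: "proportion of participants with clinically significant change in BPI pain severity scale (30% reduction").

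**Adjustment.** Section 7.A gives age, sex and medical comorbidities as the key variables that trigger adjusted analyses when the groups differ. Aim 1 otherwise adjusts for whatever is related to the outcome in bivariate tests. Baseline BPI is not named in either place, and nothing says how a participant with a baseline score of 0 is classified.

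**The concern.** A percentage-reduction responder outcome behaves differently at different starting scores. At baseline 0 it is undefined. At low scores a one-point movement, which ordinary week-to-week rating variation can produce, is enough. At high scores it takes several points.

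In a randomised trial this would mostly add noise. Here the exposure is the capsule product that the participant obtained from the dispensary, in an observational cohort. If people with milder pain tend towards one product, the responder rates will differ even when neither product does anything. The adjustment that would counter this is left to a bivariate screen with about 42 participants per group.

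The baseline-0 case also leaves the analyst a choice between counting such people as non-responders, dropping them, or treating the outcome as missing and imputing it. These can give different Aim 1 results, and none is pre-specified.

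**Working it through.** **1. Points needed for a 30% fall.** On a whole-point scale, the requirement is the smallest k with k ≥ 0.3 × baseline.

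- Baseline 0: impossible.
- Baseline 1, 2, 3: 1 point (100%, 50%, 33%).
- Baseline 4, 5, 6: 2 points.
- Baseline 7 to 10: 3 points.

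If the subscale could take quarter-point values (an assumption), baselines 1, 2 and 3 would need 0.5, 0.75 and 1.0 points. That is still at most one point, and 0 is still impossible.

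**2. The plan's own power.** Inputs from section 3.A and Table 9: 42 per group, 40% vs 20%, two-sided 5%, ICC 0.4, stated power 84%. From section 2.C: 14 weekly follow-up scores. The plan used simulation; a design-effect approximation gives:

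- Effective n per group = 42 × 14 / (1 + 13 × 0.4) = 588 / 6.2 = 94.8.
- SE under the null = √(0.3 × 0.7 × 2 / 94.8) = 0.0666. SE under the alternative = √((0.24 + 0.16) / 94.8) = 0.0649.
- Power = Φ((0.20 − 1.96 × 0.0666) / 0.0649) = Φ(1.07) = 0.858, within two points of the stated 84%.

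The same method gives 0.927 at ICC 0.3 (stated 0.91) and 0.979 at ICC 0.2 (stated 0.97). A single week-14 comparison of 42 vs 42 gives 0.516, so the stated power rests on the repeated measures.

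**3. Effect of a share f at baseline 0 (assumed, equal in both groups), ICC 0.4.**

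- Dropped (effective n = 94.8 × (1 − f), rates unchanged): f = 10% gives n = 85.4 and power 0.819; f = 20% gives n = 75.9 and power 0.772.
- Kept as non-responders (rates × (1 − f)): f = 10% gives 36% vs 18% and power 0.802; f = 20% gives 32% vs 16% and power 0.736.

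**4. Chance response with no true change.** Assume an error-free baseline, normal rating noise with standard deviation s, and rounding to whole points. A response then needs noise below −0.5 at baseline 1-3 and below −1.5 at 4-6, so the probabilities are Φ(−0.5/s) and Φ(−1.5/s).

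- s = 0.5: 16% at 1-3; 0.1% at 4-6.
- s = 1: 31%; 6.7%.
- s = 2: 40%; 23%.

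**5. What an imbalance could do.** Suppose neither product has an effect, 50% of one group and 10% of the other start at 1-3, and everyone else starts at 4-6 (all assumed). The spurious gap is (0.50 − 0.10) × (chance rate at 1-3 − chance rate at 4-6).

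- s = 0.5: 0.4 × (0.159 − 0.001) = 6 points.
- s = 1: 0.4 × (0.309 − 0.067) = 10 points (19% vs 9%).
- s = 2: 0.4 × (0.401 − 0.227) = 7 points.

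The planned difference is 20 points.

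**6. Cost of restricting the main analysis to baseline ≥4.** On the basis of step 2, with 40% vs 20% unchanged, removing 20%, 30% or 40% of participants leaves power of 0.772, 0.715 or 0.647.

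**The case against.** Several counter-arguments have force.

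- **Frequency is unknown.** The cohort is people with neuropathic pain who are certified and intend to obtain a new product. Section 4.A says that most of those certified have pain. Section 1.B lists HIV as a qualifying condition for certification, so a score of 0 is possible, but nothing in the documents supports a particular share such as 10% or 20%. This stands: the power figures are illustrations.
- **The questionnaire route may not be lenient.** The documents do not give its scoring, so a threshold above 0 cannot be judged either way. This stands. The gap comes from the three record-based routes and the absence of any BPI criterion.
- **The literal primary outcome is change in BPI severity.** A reader might infer that the primary outcome itself is undefined at baseline 0. It is not: change in score exists at every baseline. The problem is confined to the 30% responder definition, which nevertheless carries the stated group comparison and the power calculation.
- **Bivariate testing may bring baseline BPI in.** It may, but it may also miss it in a sample this small, and adjustment cannot define a percentage fall from 0. The point stands in part.
- **A cut at 4 or an entry minimum has its own cost.** Step 6 shows that the loss of power can match or exceed the problem. A cut also departs from the intention-to-treat principle in section 7.A, invites regression to the mean, and leaves chance response uneven above it (6.7% at 4-6 and 0.6% at 7-10 for s = 1). This stands, and rules out making either the main remedy.

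**Conclusion.** The point holds in a limited form. Entry permits any baseline BPI, the responder definition depends strongly on baseline BPI, the groups are not randomised, and the plan neither guarantees adjustment for baseline BPI nor says what happens at 0. A baseline imbalance can therefore bias the Aim 1 responder comparison.

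The size cannot be fixed from the documents. If 10% or 20% score 0, power at ICC 0.4 goes from about 86% to 82% or 77% (dropped), or to 80% or 74% (counted as non-responders). Chance response at baseline 1-3 runs from about 16% to 40% over rating SDs of 0.5 to 2. The shares, the SDs and an error-free baseline are all assumptions.

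A reader might infer that the study is underpowered because of low-pain entrants, or that chance response among them exceeds the 20% predicted for the high-CBD group. The documents support neither. The first needs a baseline distribution that is not given. The second depends on the assumed SD (it fails at 0.5) and compares a subgroup of unknown size with a whole-group rate.

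**What to change.** Amend section 7.A as follows.

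- Include baseline BPI severity as a covariate in the Aim 1 mixed-effects logistic model in every case, whatever the bivariate tests show, and add it to the listed key variables.
- Exclude baseline-0 participants from the 30% responder analysis, where the outcome is undefined. Add a sensitivity analysis that counts them as non-responders, and report their number by product group. They stay in all score-based analyses.
- Report a restriction to baseline BPI of 4 or more (the lowest whole score at which response needs more than one point) as a sensitivity analysis only. No entry minimum is needed.

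The cost is SAP wording: baseline BPI is already collected and no visit or measurement is added. The downside is slightly fewer participants in the responder analysis. Adjustment deals with imbalance in baseline pain only, not with other differences between people who obtain different products.

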Individuals who do not qualify for the study due to exclusion criteria #3, 7, or 9, can choose to cease medical cannabis for a 30-day wash-out period (confirm with self-report, PMP and urine drug screen); cease unregulated cannabis, cocaine, opioid, or benzodiazepine use for 30 days (confirmed with self-report and urine drug screen); and/or cease NSAID use for 7 days (self-report). Once they have done this, they can screen for the study again and may be eligible.

Recruitment will occur via Vireo and Montefiore staff referrals. Letters can also be mailed to potential participants in which information will be provided about the study. Flyers will be posted at Vireo dispensary facilities as well as online. We will recruit 3-4 participants per month for 36 months (total sample size of 100). Recruitment will be feasible, as Vireo has over 100 new patients per month. Also, we will utilize the CFAR database to assist with recruitment for this study.

Screening will occur by phone after obtaining oral informed consent. The screening questionnaire will include some questions related to eligibility criteria and others unrelated to eligibility criteria. We will obtain oral consent to review patient's PMP at the same time that we conduct the screening questionnaire. We will schedule eligible participants for a baseline visit and written informed consent will be obtained. In-person screening will occur at Montefiore and Einstein.

Participant tracking. My mentors have extensive experience following populations in studies with follow-up rates of 84%-86% over 6-12 months. At all visits, we will record: 1) participants' address and phone numbers; 2) contact information of family or friends; and 3) locations where participants work or "hang out."

Dispensed opioids or benzodiazepines within 60 d	PR
Non-steroidal anti-inflammatory use within 7 d prior to enrollment	SQ, PR
Steroid use within the past 14 d with duration of therapy ≥ 21 d	SQ, MR
COVID vaccination or booster within 14 days of screening	SQ, MR
SQ=screening questionnaire, MR= medical record, PR=pharmacy records or PMP, TQ=telephone questionnaire; U=urine sample	

Aim	Construct	Measure	Source
Main independent variable			

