Aims 1-4	Medical cannabis use	Initial soft-gel capsule dispensed at Vireo Certification for medical cannabis (date, doctor, conditions) All medical cannabis products dispensed (date, product, dose, amount dispensed) Self-reported medical and unregulated cannabis use (product, # of days used, route, dollar amount of unregulated cannabis purchased, ASI)	PR MR PR TQ
Primary outcome variables			
Aims 1, 4	Pain Severity	Brief Pain Inventory (BPI) Severity subscale ⁹⁰	TQ
Secondary outcome variable			
Aims 2, 4	Inflammatory cytokines	Pro-inflammatory cytokines (TNF α , IL-6) Anti-inflammatory cytokines (IL-4, IL-10)	B B
Aims 3, 4	Adverse events	VL, CD4 count AIDS Clinical Trial Group (ACTG Adherence) ⁹³ , Visual Analog Scale (VAS) ⁹⁴ ARVs dispensed Depression (Center for Epidemiological Studies-Depression Scale [CES-D])), Generalized Anxiety Disorder (GAD-7) ⁹⁶	B IQ PR IQ
Other measures			
Aims 1-4	Sociodemographics	Age, race/ethnicity, education, insurance, sex, gender	IQ
Aims 1-4	Pain characteristics	Brief Pain Inventory (BPI) Interference subscale ⁹⁰ Pain catastrophizing scale ⁹⁸ , Pain DETECT questionnaire ⁸⁴	IQ IQ
Aims 1-4	Pain treatment	Pain treatment (SSRIs, gabapentin, injections, physical therapy)	IQ/MR/PR
Aim 3	Substance use/disorder	Smoking (Fagerstrom test for nicotine dependence) ⁹⁹ , Alcohol Use Disorders Identification Test (AUDIT) ¹⁰⁰ , ASI ⁹⁷	IQ
Aim 3	HIV Risk Behaviors	HIV risk behaviors (HIV Risk-taking Behavior Scale ¹⁰¹⁻¹⁰³)	IQ
Aims 3, 4	Psychiatric symptoms	PTSD Checklist (PCL), ¹⁰⁴ Insomnia severity index, ¹⁰⁵	IQ
Aims 1, 3, 4	Quality of Life	Roland Morris Disability Questionnaire ¹⁰⁶ , Patient Reported Outcomes Quality of Life-HIV (PROQOL-HIV) ¹⁰⁷	IQ
Aims 1-4	Medical comorbidities	Comorbidities (obesity, cardiovascular disease, diabetes)	MR
Aims 1-4	Side effect vs benefit	Treatment Satisfaction Questionnaire for Medication (TSQM-9) ⁹¹	TQ
Aims 1-4	Urine cannabinoid	Urine GCMS for cannabinoids	

B=blood test; MR=Medical records; PR=Pharmacy records or Prescription Monitoring Program; IQ= in-person questionnaire; TQ=phone questionnaire; SSRI=selective serotonin reuptake inhibitor; TQ measures occur every week; IQ occurs at 0 and 14 weeks. B occurs at 0 at 14 weeks.

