Medical record data will be extracted 6 months prior to enrollment through 14 weeks after enrollment, including medical cannabis certification forms, prescriptions, and notes regarding pain treatment (nerve blocks, physical therapy, occupational therapy).

Pharmacy and PMP records will be extracted for medications dispensed 6 months prior to enrollment to 14 weeks after enrollment. Data will include ARVs, controlled substances (e.g., dispensed medical cannabis products, THC and CBD content in milligrams, doses dispensed) and pain medications (i.e., anticonvulsant, selective serotonin reuptake inhibitor, topical lidocaine).

Blood draws: Approximately 15 ml of blood will be drawn to assess VL, CD4 count, pro-inflammatory and anti-inflammatory cytokines. *VL and CD4 count* will be processed through Montefiore's central lab. VL will be quantified using the Abbott RealTime HIV-1 Viral Load assay (Abbott Park, Illinois), and CD4 count will be measured by the BD Multitest (BD Biosciences, San Jose). *Pro- (TNF α , IL-6) and anti- (IL-4, IL-10) inflammatory cytokines* will be analyzed using the Olink cytokine assay (Thermo Fisher Scientific, Waltham, MA) at Mount Sinai's Human Immune Monitoring Center.

Urine samples: We will check urine drug screens to confirm that patients are taking medical cannabis and to confirm that they abstain from opioid use during the course of the study.

4) Recruitment

4.A. Recruitment will occur from Montefiore's Medical Cannabis Program in which 25 patients are certified per month. Of those, approximately 6 are PLWH. In June 2020, [name] expanded the program to include Montefiore's HIV clinic, where 2500 PLWH receive care. With this expansion, at least 20 PLWH per month are certified for medical cannabis, and an overwhelming majority have pain. We will also leverage the clinical core of the ERC-CFAR to identify and recruit PLWH with neuropathic pain. Through these targeted clinical activities, we anticipate that enrolling 100 PLWH over 36 months (3-4/month) will be feasible.

Participant tracking: To facilitate tracking participants over 14-weeks, we will record: 1) participants' address and phone numbers; 2) contact information of family or friends; and 3) locations where participants work. This method allowed for 85% retention over 6 months of follow up in previous research studies.⁸⁵⁻⁸⁷

4.B. Participant retention

We will use previously established methods by my mentors to maximize retention in clinical trials.

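### Baseline pain and cytokines are taken after 7 NSAID-free days, but NSAID use in follow-up is not limited and not reliably recorded, so restarting an NSAID can mix into both outcomes by an unknown amount

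*Combined protocol and SAP*

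**What the plan says.** **Entry.** Section 2.C, exclusion 9, bars "non-steroidal anti-inflammatory (NSAID) use within 7 days prior to enrollment". Table 4 repeats this ("Non-steroidal anti-inflammatory use within 7 d prior to enrollment") and gives the screening questionnaire and pharmacy records as sources. The wash-out paragraph of 2.C lets people who fail this criterion "cease NSAID use for 7 days (self-report). Once they have done this, they can screen for the study again". Section 6.A places the blood draws at enrollment and week 14, so the baseline sample falls at the end of the NSAID-free window.

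**Follow-up.** The footnote to the measures table sets the timing: "TQ measures occur every week; IQ occurs at 0 and 14 weeks". The pain-treatment row of that table reads "Pain treatment (SSRIs, gabapentin, injections, physical therapy", with in-person questionnaire, medical record and pharmacy record as sources. Section 3.C describes the pharmacy and PMP extraction as covering "pain medications (i.e., anticonvulsant, selective serotonin reuptake inhibitor, topical lidocaine". It also takes prescriptions from the medical record through week 14, and lists the questionnaires' focus as pain, THC/CBD dose, psychological symptoms and ARV adherence. The only analgesic abstinence that 3.C says is checked during the study is from opioids, by urine screen.

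**Analysis.** Section 7.A, Aim 1: "A clinically significant change is 30% reduction in BPI pain severity scale". Aim 2: "We will examine how pro- and anti-inflammatory cytokines measured at 0 and 14 weeks change in participants". Aim 1 adjusts for covariates that show a bivariate association with outcome. Aim 2 names obesity, cardiovascular disease and diabetes as examples. Neither names NSAID use.

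**The concern.** The plan treats recent NSAID use as something to control at entry, then compares that controlled baseline with follow-up values under no such condition. Someone who stops a regular NSAID to qualify may rate pain higher at baseline than usual. If they restart after enrollment, the return to usual pain counts toward the 30% reduction, and the week-14 sample is taken on an anti-inflammatory drug while the week-0 sample was not.

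The products are not randomized, so nothing balances restart between the groups. People with poorer relief may restart more often, and people who choose one product may differ in NSAID habits from the outset. The product contrasts in H1 to H3 could then partly reflect NSAID use. Aim 4 is exposed too, because NSAID restart could move both the cytokine mediator and pain. Without weekly NSAID data, the analysts could not say reliably how much of a result this explains.

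**Working it through.** **1. The plan's own power figure.** Inputs from 3.A and Table 9: 40% versus 20% responders, 42 per arm, ICC 0.4, two-sided 5%, stated power 84%. With 14 weekly ratings, effective n per arm = 42 × 14 / (1 + 13 × 0.4) = 588 / 6.2 = 94.8. The two-proportion normal approximation then gives 86%, within 2 points of the stated figure. A single week-14 comparison at 42 per arm gives 52%.

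**2. How restart alone changes response.** Simulation with no cannabis effect. Assumptions, none from the documents except the 0–10 scale, the 30% rule and the value 0.4: usual pain has mean 5 or 6 and total SD 2; correlation between ratings is 0.4 or 0.7; ratings are rounded and clipped to 0–10. Baseline = usual + rebound + noise; week 14 = usual + noise. Response = week 14 ≤ 0.7 × baseline, with baseline above 0. (The plan's ICC refers to change in pain severity over time; here it serves as the correlation of raw ratings, so 0.4 is borrowed, not taken over exactly.)

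| Correlation | Usual mean | Never stopped (rebound 0) | Restart, 0.5-point rebound | Excess | Restart, 1-point rebound | Excess |
|---|---|---|---|---|---|---|
| 0.4 | 5 | 22.0% | 27.6% | 5.6 | 33.8% | 11.8 |
| 0.4 | 6 | 17.7% | 22.7% | 5.0 | 28.5% | 10.8 |
| 0.7 | 5 | 15.2% | 21.5% | 6.3 | 29.0% | 13.8 |
| 0.7 | 6 | 10.9% | 16.0% | 5.1 | 22.6% | 11.7 |

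The excess among restarters is about 5 to 6 points for a 0.5-point rebound and 11 to 14 points for a 1-point rebound.

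**3. What that does to the product contrast.** Let f be the share of an arm that stopped an NSAID to qualify and restarted, and q the chance that restart turns a non-responder into a responder. Then observed rate = p + f × q × (1 − p). From the table, a 1-point rebound implies q between 10.8/82.3 = 0.13 and 13.8/84.8 = 0.16. I use q = 0.2, slightly above that; f is assumed.

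- *Equal restart, f = 0.3 in both arms.* If both products truly have 20%, both show 0.20 + 0.3 × 0.2 × 0.8 = 24.8%, and the false-positive rate stays at 5%. If truth is 40% versus 20%, the observed rates are 43.6% and 24.8%. The difference falls from 20 to 18.8 points, and power at effective n 94.8 falls from 86% to 78%.
- *Unequal restart, f = 0.1 (high THC) and 0.4 (high CBD).* If both are truly 20%, the observed rates are 21.6% and 26.4%, and the false-positive rate is 8% at 42 per arm (12% at 94.8). If truth is 40% versus 20%, they are 41.2% and 26.4%: the difference is 14.8 points and power at 94.8 is 58%.
- *Shares reversed, f = 0.4 and 0.1.* High THC shows 0.40 + 0.4 × 0.2 × 0.6 = 44.8% and high CBD 21.6%. The difference widens to 23.2 points.
- *A mild case.* Shares of 10% (high THC) and 30% (high CBD), each restarter adding 5 points: 40 + 0.10 × 5 = 40.5% versus 20 + 0.30 × 5 = 21.5%. The difference is 19.0 points, and week-14 power at 42 per arm goes from 52% to 47%.

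**4. Cytokines.** False contrast = difference in week-14 NSAID use × NSAID effect. With an assumed 30-point difference and 0.5 SD effect, 0.30 × 0.5 = 0.15 SD, which is 30% of the d = 0.5 used in 3.A. Over 10 to 40 points and 0.25 to 0.75 SD, the range is 0.10 × 0.25 = 0.025 to 0.40 × 0.75 = 0.30 SD.

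**The case against.** **Some NSAID use may be captured already.** A reader might infer that NSAID use in follow-up cannot be detected at all. The documents do not support that. The pain-treatment row has a participant questionnaire among its sources at weeks 0 and 14, and its list may be examples, since it differs from the list in 3.C. Table 4 already uses pharmacy records for NSAIDs at entry, and record prescriptions run to week 14. This stands. What remains is that no follow-up source names NSAIDs, records would miss over-the-counter use, and nothing gives weekly timing.

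**Restart alone does not create a product difference.** This also stands. Equal restart leaves the false-positive rate at 5%. A false contrast needs restart to differ by product, and the likeliest story, more restarting where relief is poor, would pull the planned difference toward zero if high CBD relieves less.

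**Restart after poor relief is a consequence of the product.** Under the intention-to-treat principle in 7.A, including it is a defensible treatment-policy choice. That is why the main analysis should stay as it is and any NSAID-based scoring should be labelled a different estimand.

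**Larger figures are possible but less apt.** Comparing restarters with people who stopped and stayed off gives 14 to 18 points for a 1-point rebound. Part of that gap arises because a persistently higher pain level makes a 30% fall harder to reach. On whole-number ratings, a return from 7 to 5 is a 28.6% fall and not a response, so for someone whose usual rating is 5, rebound alone must reach 3 points.

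**Steroids and COVID vaccination are not the same problem.** The wash-out paragraph in 2.C offers a stop-and-re-screen route for exclusions 3, 7 and 9 only, so that route does not lead anyone to stop steroids to qualify. The vaccination rule is timed to screening.

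**Conclusion.** The point holds on the text: an NSAID-free baseline, a route that brings in people who have just stopped an NSAID, no limit on follow-up use, and no follow-up list that names NSAIDs. Restart can therefore raise 30% responses or shift week-14 cytokines without a cannabis effect. It dilutes the product contrast if restart is equal, and biases it in either direction if not.

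The size cannot be derived from the documents, which give no share using the wash-out, no restart rate, and no NSAID effect on neuropathic pain or these cytokines. Under the stated assumptions, a 0.5 to 1 point rebound adds about 5 to 14 points of response among restarters compared with people who never stopped. The effect on the contrast ranges from about 1 point in the mild case to about 5 points under a heavy 10% versus 40% imbalance.

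This does not show that the planned comparison is invalid or that a false H1 result is likely. It is a gap in data collection that is cheap to close now and hard to repair later.

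**What to change.** 1. Add one item to the weekly questionnaire: number of days with NSAID use in the past week. At the week-14 visit, before the blood draw, repeat the screening questions on NSAIDs, steroids and vaccination. For the last two this is a check that the week-0 and week-14 samples are comparable.
2. Carry an indicator for having stopped an NSAID to qualify, from screening, into the Aim 1 and Aim 2 models as a baseline covariate. It is fixed before exposure, so adjusting for it adds no post-exposure bias.
3. Keep the main analysis as planned and prespecify two supporting sensitivity analyses. For Aim 1, take account of weeks with reported NSAID use, for example by scoring them as non-response; label this a different estimand and note that it also counts NSAIDs taken for unrelated reasons. For Aim 2, restrict to participants whose week-14 sample meets the entry conditions on NSAIDs, steroids and vaccination.

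**Cost.** One extra item in a 5–7 minute questionnaire, three repeated questions, one covariate and two analyses. Participants already followed will lack the weekly item, though the screening indicator may still be recoverable for them. The restricted Aim 2 set is smaller and selected on post-baseline behaviour, so it can support the main analysis but not replace it. No change to what participants may take is proposed.
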